10.5. Appendix 5: Derived and Transformed Data

10.5.1. General

Multiple Measurements at One Analysis Time Point

- Mean of the measurements will be calculated and used in any derivation of summary statistics but if listed, all data will be presented.
- If there are two values within a time window the value closest to the target day for that window will be used. If values are the same distance from the target, then the mean will be taken.

Study Day

- Calculated as the number of days from First STM Dose Date:
 - Ref Date = Missing → Study Day = Missing
 - Ref Date < First STM Dose Date → Study Day = Ref Date First STM Dose Date
 - Ref Data ≥ First STM Dose Date → Study Day = Ref Date (First STM Dose Date) + 1

Age

Age = Screening date – Date of Birth
 Date of birth will be imputed based on the assumption that all subjects were born on the 30th June (30 Jun YYYY).

Baux score

Baux score: Age + % Total Body Surface Area (TBSA) burned

10.5.2. **Efficacy**

Fractional Excretion of Lactulose/Mannitol/Sucralose

Data is provided to S&P in the form of quantity of material in micrograms/litre, based on a sample of urine.

Fractional excretion (FE) of lactulose or mannitol or sucralose = (urine concentration (micrograms/litre) × total urine volume excreted in litre) / probe input (micrograms).

Where,

- Urine concentration is provided in the BIOMARKER dataset,
- Urine volumes excreted are provided in the BIOLINK dataset,
- Probe input refers to the total STM taken (as per Table 7.1 of the protocol-5g Lactulose, 2g Mannitol and 2g Sucralose)

Urine concentration in the BIOMARKER dataset will be provided at two timepoints per visit (0-5hr) and (0-24hr)

FE will be calculated for timepoints 0-5 and 0-24 hours for Lactulose, Mannitol and Sucralose.

For calculations of the 0-24 FE's, total urine volume will be based on the following:

Total urine=urine excreted 0-5 hrs + urine excreted 5-24 hours.

Note: If urine excreted 0-5 hrs is missing then total urine should be considered missing.

Note: 1g=1000000 micrograms

L/M ratio

L/M ratio = FE lactulose / FE mannitol

Healthy Participant – Average

• Average = Mean of all data available at all timepoint for each healthy participant.

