gastric emptying, and degradation in the large bowel by commensal bacteria; thus, a monosaccharide such as mannitol, which passes freely across the healthy intestinal barrier, is often co-administered to 'normalise' lactulose measurements. Following administration of both lactulose and mannitol the fractional excretion of the sugars is expressed as a ratio where mannitol is the denominator. Lactulose and mannitol absorption occurs mainly in the proximal small intestine and is complete within approximately 5 hours of oral administration. This approach has been previously used successfully in patients with severe burn injury and intestinal permeability was found to correlate with episodes of sepsis [Doig, 1998].

In order to assess the permeability of the large bowel a third oligosaccharide, sucralose, will also form part of the sugar absorption test. This synthetic sweetener (marketed by Tate and Lyle as 'Splenda') is not subject to the same degradation by large bowel commensal flora as lactulose and is therefore a better measure of large bowel permeability than lactulose. Again, this has formed part of previously described studies aiming to measure intestinal permeability [Del Valle-Pinero, 2013].

Lactulose, mannitol and sucralose will be co-administered to both healthy participants and participants following thermal injury. In order to document accurately the time course of change in permeability, thermally injured participants will be asked to undergo the test on alternate days for 14 days (the intense monitoring phase) followed by two convalescent samples at day 28 and month 6 (thermal injury participants). In order to produce an accurate baseline measurement, healthy participants will be asked to undergo three measurements of intestinal permeability over approximately a two week period.

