7. NON-INVESTIGATIONAL MEDICINAL PRODUCT (NIMP)

A study treatment is defined as any investigational treatment(s), marketed product(s), placebo, or medical device(s) intended to be administered to a study participant according to the study protocol. According to this definition, no GSK study treatment will be employed in this study.

The STM (comprising lactulose, mannitol and sucralose) will be intermittently administered enterally as a study challenge agent to measure permeability at different points along the GI tract. Lactulose and Mannitol assess small intestine permeability and sucralose to assess colonic permeability.

It is important to note that the administration of the STM is not therapeutic (lactulose and mannitol can be used as laxatives, however the amount in the STM is sub-therapeutic) and as such should be regarded as a non-investigational medicinal product (NIMP) [[Guidance Documents Applying Investigational Medicinal Products \(NIMPS\)](#), 2011].

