9.10.3. Urine Sample Collection

- Urine samples will be collected as a part of the measurement of intestinal permeability which is described in Section 9.4.
- Additional urine samples will be collected from patients as part of the SIFTI-2 study to which all thermally injured participants will be co-recruited. These will be used for, among other tests, the quantification of protein and microbial metabolites.
- It is standard practice that patients admitted with burns of TBSA $\geq 15\%$ will have a urinary catheter inserted on admission to ensure the accurate maintenance of fluid balance. A clean urine sample will be taken from the appropriate port on the urinary catheter. In patients who are not catheterised, a mid-stream urine (MSU) should be collected in a clean universal container where possible.
- N.B. During the 24 hours following STM administration (during intestinal permeability measurement) urine samples must only be taken from the 5-hour of 24-hour urine collections **after** the aliquots for sugar quantification have been taken.

Sample Preparation

- Details of urine sample collection, processing, storage and shipping procedures are provided in the SRM.

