1. SUMMARY OF KEY PROTOCOL INFORMATION

1.1. Changes to the Protocol Defined Statistical Analysis Plan

This study was terminated prior to the full sample size being achieved. As a result the initially planned sample size of 25 for the thermally injured subjects is greatly reduced to 3. Changes from the originally planned statistical analysis specified in the protocol (Dated:26SEP2017) are outlined in Table 1.

Table 1 Changes to Protocol Defined Analysis Plan

Pro	Protocol		Reporting & Analysis Plan				
Sta	tistical Analysis Plan		Statistical Analysis Plan		Rationale for Changes		
•	Co -Primary Objective 1: To determine the impact of thermal injury on the magnitude of small intestinal permeability change as soon as possible following injury compared to healthy participants.	•	Summary statistics for Lactulose/Mannitol (L/M) ratio at entry will be provided. No formal stats analysis for comparing the groups.	•	No stats analysis due to limited sample size.		
•	Exploratory objective 1: Comparison of Fractional excretion of sucralose of TI participants with Healthy participants at baseline	•	Only summary will be provided. No formal stats analysis for comparing the groups.	•	No stats analysis due to limited sample size.		
•	 Exploratory objective 3: Number of ventilator-free days, vasopressor-free days, hemofiltration-free days, episodes of confirmed infection and sepsis, surgical interventions Total length of hospital stay Calculate critical care and thermal injury severity scores 	•	None of the endpoints will be analysed for final reporting.		 Due to limited sample size, these endpoints will not be analysed. Where relevant, these will be described using data from the SIFTI2 CRF in CSR. 		
•	Exploratory objective 4: Change in urine protein: creatinine and urine albumin: creatinine ratios	•	This endpoint will not be analysed.	•	The reason for collecting these data was to inform a pharmacokinetic model. As development of the molecule has been terminated, this model is no longer required, moreover data collected are so limited that analysis is not possible.		
•	Exploratory objective 5: Changes in microbiome of acute and convalescent stool samples	•	This endpoint is not considered for final analysis.	•	Only one stool sample has been collected from a TI patient thus no meaningful comparison is possible.		

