1.2.2. Final Reporting Objectives & Endpoints Following Study Termination

	jectives	Endpoints			
Pri	mary Objectives	Primary Endpoints			
•	To determine the impact of thermal injury on the magnitude of small intestinal permeability change as soon as possible following injury compared to healthy participants	Lactulose/Mannitol (L/M) ratio at entry			
•	To characterise the effect of thermal injury on small intestinal permeability over time and establish the clinical and demographic factors which can influence it	Changes in L/M ratio over time			
Ex	ploratory Objectives	Exploratory Endpoints			
•	To determine the impact of thermal injury on colonic permeability as soon as possible following injury compared to healthy participants	Fractional excretion of sucralose at entry			
•	To characterise the effect of thermal injury on colonic permeability over time	Changes in the fractional excretion of sucralose over time			
•	To assess plasma and urine biomarkers of intestinal permeability and bacterial translocation	Change in markers of intestinal mucosal damage samples from blood			
		Change in bacterial markers of translocation			
•	To assess the impact of pre-existing co-morbid conditions on intestinal permeability and clinical outcome following thermal injury	Medical history and drug history at the time of admission			

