6.2.2. Summary Measure

Absolute, Change and %Change in the fractional excretion of sucralose over

time.

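### Must the SAP name a urine window, or derive a 5–24 h increment, before sucralose can serve the colonic objectives?

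*SAP*

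**What the plan says.** SAP 1.2.2 retains a colonic objective at study entry and a second one, "To characterise the effect of thermal injury on colonic permeability over time". The endpoints are sucralose FE at entry and its change over time, with no window attached. SAP 6.2.2 gives the summary measure as "Absolute, Change and %Change in the fractional excretion of sucralose over" time, again with no window.

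SAP 10.5.2 (Efficacy) is the only place where windows are set: "FE will be calculated for timepoints 0-5 and 0-24 hours for Lactulose, Mannitol and Sucralose". Two concentrations are supplied per visit, 0–5 h and 0–24 h. The 5–24 h interval appears only as a urine volume, added to the 0–5 h volume to give the 24 h total.

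Tables 2.4–2.6 are paged by timepoint and Figures 2.4–2.8 are plotted by timepoint. The shells in SAP 10.9 show 0–5 h and 0–24 h. Listing 24 covers the sucralose data. For sucralose at entry, SAP 1.1 says: "No formal stats analysis for comparing the groups".

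On the role of the sugars, protocol section 7 says: "Lactulose and Mannitol assess small intestine permeability and sucralose to assess colonic permeability". Protocol 3.2.2 says: "Lactulose and mannitol absorption occurs mainly in the proximal small intestine and is complete within approximately 5 hours of oral administration". It prefers sucralose for the large bowel because it "is not subject to the same degradation by large bowel commensal flora as lactulose".

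**The concern.** Sucralose is the colonic probe, yet the plan treats all three sugars alike and shows two windows without saying which answers the colonic question. The first, 0–5 h, is the small-bowel phase as the protocol describes it for lactulose and mannitol. The second, 0–24 h, contains that phase. The protocol's reason for choosing sucralose is that colonic bacteria do not degrade it in the same way. That is not a statement that the small bowel does not absorb it.

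The study expects burns to raise small-bowel permeability. If any sucralose crosses there, 0–24 h FE would rise with no colonic change, and a reader of that page alone could call the rise colonic. The difference FE(0–24) − FE(0–5) looks like the natural remedy, and no display plans it. With two undesignated windows, the one called colonic could also be picked after the data are seen.

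**Working it through.** The documents give no figure for sucralose by window, so there is none to reproduce. The check takes the definitions and then a mass balance under stated assumptions.

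**Inputs from the documents.** FE is derived for 0–5 h and 0–24 h (SAP 10.5.2). There are 3 injured participants (SAP 1.1). The study ended before anyone reached day 28 (SAP 1.3). Seven permeability tests are scheduled in the first 14 days (protocol 2.2).

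**Assumptions, not in the documents.** Let s be the small-bowel share of healthy 24 h sucralose recovery, k the small-bowel fold change, m the colonic fold change, and l the fraction of small-bowel sucralose excreted after 5 h. All colonic sucralose is taken to appear after 5 h.

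**Size of the possible misreading.** The 0–24 h ratio is k·s + m·(1 − s). With k = 3 and m = 1 this is 1 + 2s. A purely colonic change giving the same ratio has m = (1 + s)/(1 − s).

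| s | 0–24 h ratio, colon unchanged | Colonic fold giving the same ratio |
|---|---|---|
| 0 | 1.00 | 1.00 |
| 0.1 | 1.20 | 1.1/0.9 = 1.22 |
| 0.3 | 1.60 | 1.3/0.7 = 1.86 |
| 0.5 | 2.00 | 1.5/0.5 = 3.00 |

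For s above zero, 0–24 h FE alone cannot separate the two causes. At s = 0 there is nothing to separate.

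**Does the increment help?** With the same l in both groups, the 5–24 h ratio is (k·s·l + m·(1 − s))/(s·l + 1 − s). At s = 0.3:

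- l = 0: small-bowel cause 1.00, colonic cause 1.86
- l = 0.2: 0.88/0.76 = 1.16 against 1.36/0.76 = 1.79
- l = 0.4: 1.06/0.82 = 1.29 against 1.42/0.82 = 1.73

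The contrast is sharper, but only while l is equal in the two groups. Protocol 3.2.2 names gastric emptying and renal function as influences on lactulose recovery. Protocol 7.1 allows swallowed capsules or opened capsules given by tube. Suppose instead that l = 0 in healthy participants and l > 0 in injured ones. With s = 0.3, k = 3 and an unchanged colon, the 5–24 h ratio is (0.9·l + 0.7)/0.7:

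- l = 0.2: 0.88/0.7 = 1.26
- l = 0.4: 1.06/0.7 = 1.51
- l = 0.5: 1.15/0.7 = 1.64

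It passes the 1.60 of the 0–24 h window once 0.9·l exceeds 0.42, that is l above about 0.47.

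**Noise of a difference.** Let r = FE(0–5)/FE(0–24), with independent 10% errors on each amount. The CV of the increment is 0.1·√(1 + r²)/(1 − r): 11% at r = 0.1, 22% at r = 0.5 and 64% at r = 0.8. In the last case about 6% of values would be negative.

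**What is already recoverable.** The injured group has at most 3 × 7 = 21 scheduled tests, so at most 21 subtractions. The percent-change pages alone would not suffice. A rise of 200% at 0–5 h with 60% at 0–24 h implies (60 − 200r)/(1 − r) at 5–24 h, where r is the baseline ratio: 44%, 25% or 0% for r = 0.1, 0.2 or 0.3. Individual absolute values do suffice, and Listing 24 covers them.

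**The case for a change.** The best case for a change is that it is cheap. One sentence could name the window, and one derived variable could show the increment. Naming the window beforehand would stop the author choosing the more interesting one. The SD, median, range and percent change of the increment cannot be had from Tables 2.4–2.6, and with so few patients the individual curves are the main evidence, so their labels matter.

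Part of this stands. No window is designated, no increment is planned, and the conditional arithmetic is right. But both windows are reported, so a selective reading would be visible. Missing summary statistics for 3 people are a small loss when sucralose data are listed by subject. If the small bowel alone changed, the rise would also show on the 0–5 h page.

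The increment needs care too. The subtraction is valid only if the 0–24 h concentration comes from pooled urine. The SAP formula implies this, but protocol 9.10.3 says only that further "urine samples must only be taken from the 5-hour of 24-hour urine collections", and the detailed method is in the Study Reference Manual, which was not available. New rules for negative values and unstable percent changes would also be needed.

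**Conclusion.** No change to the plan follows. The gap is missing detail, not a rule that yields a wrong result. The protocol assigns sucralose to the colon, and its roughly 5 h completion time is given for lactulose and mannitol only. An analyst would naturally read 0–24 h sucralose beside 0–5 h, and the planned displays give both.

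The possible misattribution runs from none to a 2.00-fold rise in 0–24 h FE. That rests wholly on an assumed small-bowel share of 0–50% and an assumed threefold small-bowel rise. Making the 5–24 h increment the preferred colonic measure would exchange one unverified assumption (no small-bowel uptake) for another (equal excretion timing in burned and healthy participants), and would add noise.

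The endpoint is exploratory and descriptive, with 3 injured participants and no formal group comparison, and SAP 1.1 records that development of the molecule has ended. No conclusion would change. If the report comments on the colon, the author can note that 0–24 h FE may include small-bowel uptake.

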3.2. Background

3.2.1. Thermal Injury, Intestinal Permeability and Multi-Organ Dysfunction Syndrome

Patients with severe thermal injury >20% TBSA are at risk for organ dysfunction and may develop multiple organ dysfunction syndrome (MODS). This study aims to explore the relationship between thermal injury, changes in intestinal permeability and the onset of MODS.

One of the central hypotheses over the last two decades to explain the onset of MODS in the context of critical illness imputes that an increase in intestinal permeability results in the translocation of bacteria and bacterial products to the systemic circulation where they drive inflammation and injury to distal organs [Deitch, 2006]. This hypothesis is supported by data showing that there is a significant increase in intestinal permeability in critically ill patients, including patients with thermal injury, and that the degree of intestinal permeability correlates with the onset and severity of MODS [Doig, 1998]. As such, therapies directed at minimising these changes in intestinal permeability, thereby limiting the translocation of bacteria to the systemic circulation, are hypothesised to have an impact on clinical outcome in these patients (Figure 1).

Figure 1 Changes in Intestinal Permeability

[figure not shown]

Figure 1 (Left panel) Hypothesis: The gut is the major driver of MODS in critical illness (Right panel) Correlation between intestinal permeability as measured by lactulose/mannitol ratio and the severity of MODS in critically ill patients. Intestinal permeability was determined by measuring the differential absorption of lactulose (increased in the damaged gut) and mannitol (freely absorbed in the normal and damaged

gut) following oral administration and expressed as the ratio of lactulose to mannitol (L/M) [Olquin, 2005].

There are some data showing that patients with severe thermal injury (>20% TBSA) display a significant and rapid increase in intestinal permeability that declines gradually over a two-week period following the injury [Olquin, 2005]. Additionally, these changes in intestinal permeability, correlate with the severity of sepsis observed in these patients [Ziegler, 1988].

The central hypothesis of this study is that thermal injury alters intestinal barrier function allowing the translocation of bacteria and bacterial products to the systemic circulation where they contribute to the onset of MODS.

The aims of the study are:

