The STM will be prepared for administration on the assessment day and will not be sterile.	There is a risk that the sugar test material formulation may be contaminated with yeast or bacteria. The presence of contamination within the STM formulation delivered via the feeding tube in thermal injury participants could present an infection risk.	Microbiology release testing will be conducted by Tayside pharmaceuticals. The STM will be prepared on the assessment day to minimise this risk. Lactulose/Mannitol will be refrigerated from the point of manufacture and until use. The site investigators have been consulted on this risk and felt that it was low.
Incomplete 24 hour urine collections	Ambulant, uncatheterised patients and healthy participants 24-hour urine collections could be incomplete.	Ambulant, uncatheterised patients and healthy participants will receive careful education and written instructions of the importance of complete urine collections. In addition, documentation of incomplete collection, in addition to sampling collection times, will be recorded.

Potential Risk of Clinical Significance	Summary of Data/Rationale for Risk	Mitigation Strategy
Phlebotomy for biomarkers (healthy participants)	Phlebotomy can be painful and result in bruising, bleeding and puncture site infection.	Phlebotomy from thermally injured participants will not be conducted as a part of this protocol. Healthy participants will undergo one blood draw during screening and a further draw on day one. Phlebotomy will be performed by an appropriately trained member of the site study team with aseptic non-touch technique to avoid infection.

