3. ANALYSIS POPULATIONS

Population	Definition / Criteria	Analyses Evaluated
Screened	All participants who were screened for eligibility	Study PopulationAll Listings
Safety	Comprise of all participants who receive at least one dose of STM and have at least one post-dose safety assessment.	Safety
Evaluable	Comprises of all participants in the safety population excluding any healthy volunteers that received any concomitant medication or food and drink containing STM (lactulose, mannitol and sucralose), as identified by review of the protocol deviations.	EfficacyBiomarkerStudy Population

NOTES:

 Please refer to Appendix 8: List of Data Displays which details the population to be used for each display being generated.

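### SAP 10.5.2 has no rule for a urine collection documented as incomplete, so lost urine is reported as low sucralose excretion

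*SAP*

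**What the plan says.** SAP Section 10.5.2 defines FE for each sugar as urine concentration times total urine volume, divided by the amount given (2 g for sucralose). FE is derived for 0-5 and 0-24 hours. For the longer window, "Total urine=urine excreted 0-5 hrs + urine excreted 5-24 hours". One safeguard follows: "Note: If urine excreted 0-5 hrs is missing then total urine should be considered missing". Nothing is said about a missing 5-24 hour volume, or about a volume that is present but known to be short.

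The protocol foresaw short collections. Section 3.3.1 lists the risk: "Ambulant, uncatheterised patients and healthy participants 24-hour urine collections could be incomplete". The mitigation there is education, written instructions and a record of any incompleteness. Section 9.8 calls accurate capture of the whole 24-hour volume critical. Section 6.6.1 adds a planned source of partial collections: if a restricted sugar cannot be avoided, the test stops, but urine collected beforehand may still be analysed.

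The setting differs by group. Healthy participants do the test at home (Section 2.1). Patients with burns of at least 15% TBSA, as standard practice, "will have a urinary catheter inserted on admission to ensure the accurate maintenance of fluid balance" (Section 9.10.3).

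No population rule catches the problem. The SAP's Evaluable population (Section 3) is the Safety population "excluding any healthy volunteers that received any concomitant medication or food and drink containing STM". It drops the protocol's requirement for evaluable L/M measurements (Protocol 10.4) and excludes nobody for incomplete urine.

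**The concern.** Sucralose FE serves both colonic objectives, which were retained after termination (SAP 1.2.2). It has no internal denominator, so sugar lost with an uncollected void lowers it one for one. Under SAP 10.6.2, missing data are blank fields. A short volume is not blank, so it passes as valid, even where the site has recorded that the collection was incomplete.

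The affected outputs are Tables 2.4-2.6 (absolute, change and percentage change), Figures 2.4-2.8, and the healthy average used as the reference for injured participants' profiles. With 3 injured participants and no model, the reading rests largely on individual profiles against that reference, so one short collection can visibly change the picture.

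**Working it through.** **The plan's own figure.** The only power figure is 89% for a threefold L/M difference (Protocol 10.2: 25 versus 15, log SD 1.15, two-sided 0.10). The noncentrality is ln 3 / (1.15 × √(1/15 + 1/25)) = 1.0986 / 0.3756 = 2.925. With 38 df this gives power 0.890 (0.900 by the normal approximation), so the figure reproduces. It concerns L/M and says nothing about sucralose.

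**Effect of lost urine on sucralose FE.** Let *f* be the share of excreted sucralose carried away in uncollected urine. Concentration times recorded volume is the amount recovered, so

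observed FE = (1 − *f*) × true FE.

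With equal true FE in the two groups:

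- apparent injured/healthy ratio = (1 − *f* injured) / (1 − *f* healthy);
- apparent change from a complete baseline in a stable participant = −100*f* %.

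The documents give no value for *f*. The range below is an assumption, read as the average loss across the affected collections.

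| Assumed loss *f* | Healthy only: 1/(1 − *f*) | Injured only: 1 − *f* | Change after complete baseline |
|---|---|---|---|
| 10% | 1.11 | 0.90 | −10% |
| 20% | 1.25 | 0.80 | −20% |
| 30% | 1.43 | 0.70 | −30% |

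Equal loss in both groups gives 1.00. A short baseline followed by complete collections gives a false rise: at 20% loss, 1/0.80 − 1 = +25%. A false threefold difference would need healthy loss of 1 − 1/3 = 67%.

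**Why the point is limited to sucralose.** The SAP sets "L/M ratio = FE lactulose / FE mannitol". The same recorded volume multiplies numerator and denominator and cancels. Lost urine also leaves the ratio unchanged if it has the same lactulose-to-mannitol mix as the urine kept.

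**Missing 5-24 hour volume.** With no rule, whether the 0-24 hour total becomes missing or falls back to the 0-5 hour volume is left to programming.

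**The case against.** **Existing review route.** SAP 3.1 requires a pre-freeze review of deviations that may lead to exclusion, and Section 2.2 requires exclusions to be confirmed. The measurement method is in the Study Reference Manual, which is not among the documents. This stands in part: a team could act on incomplete urine through that review. But the Evaluable definition gives no such ground, and excluding a participant is not the same as setting one window's FE to missing.

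**Direction.** A reader might infer that the error always favours the study hypothesis. The documents do not support that. Protocol 9.10.3 foresees uncatheterised burn patients, and loss confined to them reverses the bias.

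**Recovery.** A reader might also infer that catheter removal will produce a false recovery of the colonic barrier. That is only conditional. No removal times are given, visits from Day 28 on are not analysed (SAP 1.3), and discharge before Day 14 ends the intense phase apart from routine-care attendances on Days 8-14. The artefact needs a catheter to come out, and urine to be lost, before Day 28.

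**Wording.** It would be too strong to say that every collection is scored as complete, since a missing 0-5 hour volume is handled, or that the protocol expects under-collection. It names a possibility.

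**A ratio to mannitol.** Protocol 3.2.1 describes "mannitol (freely absorbed in the normal and damaged" gut), so FE sucralose / FE mannitol might look like a remedy. It is not a safe one. Section 3.2.2 says mannitol absorption is complete by about 5 hours, whereas sucralose is there to measure the large bowel. A later lost void could therefore remove mainly sucralose, and the ratio would fall too. Burn patients may also receive mannitol from other sources (Section 7.7).

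**Importance.** The endpoint is exploratory and descriptive, there are 3 injured participants, and development of the molecule has ended. This limits the consequence but does not make the derived value correct.

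**Conclusion.** The point holds as a gap in the derivation rule. Followed as written, the SAP reports sucralose FE from a collection documented as incomplete as a genuine low value, in the tables, the figures and the healthy average.

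The size depends on an unknown loss. At an assumed 10-30%, loss confined to healthy participants gives a false 1.11- to 1.43-fold excess in injured participants, and loss confined to injured participants gives 0.90 to 0.70. The same loss after a complete baseline appears as a 10-30% fall. The net direction is not established. The entry comparison does not depend on catheter removal; the false-recovery reading does.

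The change is worth making because it is specific and inexpensive, but its effect on the study's conclusions is limited.

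**What to change.** In SAP Section 10.5.2:

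1. Set sucralose FE for a window (0-5 or 0-24 hours) to missing in summaries, figures and the healthy average when the collection for that window is documented as incomplete. A loss in the first 5 hours affects both windows; a later loss affects only 0-24 hours. Name sucralose FE in the rule, so that L/M, which is built from the other two FEs, is not removed with it.
2. State that a missing 5-24 hour volume makes the 0-24 hour total missing, matching the existing 0-5 hour rule.
3. Keep the computed values in Listing 24 with a completeness flag, and show catheter status if it was recorded.

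The cost is SAP wording and one flag. The protocol says incompleteness is recorded, but the SAP names no dataset that holds it, and catheter status is not in the schedules of activities, so availability must be confirmed. A few FE values leave the summaries. Under SAP 4.2.1, an incomplete Day 1 collection would also remove that participant's change values for the window. Rule 2 would make the 0-24 hour L/M missing for that test, as the existing rule already does when the 0-5 hour volume is missing.
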